## **I. Adverse Event Criteria and Reporting Procedures**

Adverse or unanticipated events will be reported as required to the Boston Children's Hospital IRB by the PI according to institutional reporting requirements.

An Adverse Event refers to any untoward medical occurrence whether or not it is considered intervention-related.

As noted above, analysis of the retrospective outcomes data for the 47 BCH patients treated with ESBs demonstrates no evidence that this block type is associated with any greater risk than that demonstrated by aggregate data from the various pediatric regional anesthesia registries. Information currently available suggests that regional blockade, when performed properly, carries a very low risk of morbidity and mortality in appropriately selected infants and children.

Nevertheless, as there exist little prospective outcomes data related to the ES block, we will implement a rigorous system to follow and report any adverse events, including interim analyses by a non-blinded statistician, as described below:

### *Adverse Event Monitoring:*

Adverse outcomes will be carefully tracked for all patients enrolled in the study. Enrollment will be halted and the IRB informed by the PI if any of the following conditions are met:

- 1 of any of the following serious adverse events:
  - Patient death.
  - Pneumothorax
  - Hematoma at the site of the catheter/block—causing pain or any neurological symptoms for the patient.
  - Persistent neurologic symptoms lasting more than 3 days after a single shot block or catheter is removed.

- Local anesthetic systemic toxicity (any symptoms leading to this diagnosis by a study team participant)
- >2 of any of the following minor/moderate adverse events in aggregate:
  - Persistent bleeding at the site of the catheter insertion or block placement.
  - Leakage of local anesthetic from the catheter insertion site that leads to discontinuation of the catheter infusion.
  - Redness or superficial infection of the catheter site or site of the block placement.
  - Skin irritation at the site of the catheter insertion or block placement that results in greater than 3 cm of induration or is associated with pain.

If there is a pause for any of the above reasons, continuance of the protocol will be at the discretion of the IRB in consultation with the study team. No individual care data will be reported unless there is a serious adverse effect. Reports will be done in an aggregated fashion.

*Special note regarding ropivacaine:*

Ropivacaine use in ESB catheters is the standard for clinical management in this patient population at this institution. It is routinely used at BCH for all nerve blocks and regional anesthetics. Known potential adverse advents of this mode of delivery of this medication include hypersensitivity, allergic reaction, hypotension and cardiac arrhythmias if injected intravascularly. The presence of any of these will be assessed by the primary anesthesiologist intraoperatively and treated appropriately at the time of block placement and initial bolus and further assessed for such daily by members of the research team and Acute Pain Service. Any occurrence of a possible adverse event or events will be documented and reported to the DSMB, the IRB and the Department of Anesthesia Quality Assurance Physician as appropriate. In the event of a serious adverse event, it will be reported to the DSMB and IRB immediately and the study halted until a thorough investigation into the cause can be made.

The relative safety of ropivacaine for use in regional anesthesia is supported by the information contained the Pediatric Regional Anesthesia Network (PRAN) database. The PRAN is a consortium of major pediatric centers in North America that manages a prospective data registry on pediatric regional anesthesia. From their database, which at this time comprises more than 130,000 pediatric regional anesthetics from numerous major centers in the US and Canada, ropivacaine is documented to be used in greater than 85% of pediatric regional with a safety profile at least equivalent to, if not better than, bupivacaine.

Further, ropivacaine is very well studied in pediatrics. There is an extensive body of prospective clinical trials and clinical outcomes studies on ropivacaine pharmacokinetics, safety and clinical outcomes from infancy through adolescence. Our prescribing practices at BCH in the Regional Anesthesia and Acute Pain Services are derived from that body of PK information and consensus recommendations.

We therefore regard ropivacaine as the established standard of care for pediatric regional anesthesia and have selected it for use in this study.

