- Postoperative infusion of local anesthetic (per weight based protocol) via the nerve block catheter is initiated (the standard infusion is straight 0.2% [contact]/kg/hr with a usual combined max rate of 15ml/hr).

All patients will have access to rescue opiates as needed by means of the standard PCA/NCA demand protocols utilized at BCH. In addition, all patients will be followed by the Acute Pain Service at BCH, enabling access to additional assessment, catheter and infusion management and opioid treatment as needed 24 hours a day, 7 days a week. Floor/ICU nursing personnel are encouraged to call the Acute Pain Service if they feel pain management is not adequate in any case – this will be reinforced for patients included in this trial. In addition, one of the primary investigators will be available for consultation 24 hours a day to the Acute Pain Service for any desired consultation on study patients.

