## **E. Definition of Primary and Secondary Outcomes/Endpoints**

### **Feasibility:**

Primary:

- Feasibility: 'Feasibility' will be defined primarily as a successful intervention completion rate of 75% or greater of all subjects with no major adverse outcomes.

Secondary:

- Data integrity: Data integrity will be considered satisfactory if there is successful collection of 75% or greater of all collectible catheter follow-up data points, in aggregate, for successfully completed subjects.
- Efficiency: The treatment will be considered to have an 'efficient intervention duration' if the intervention completion time is found to be less than 40 minutes.

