## **F. Data Collection Methods**

All patients will be assigned a unique personal identifier that will not be linked to any patient identifying information. Data will be collected during the study in case report forms and then will be entered into a password-protected, secure database or automatically collected via the Regional Anesthesia Outcomes Database and uploaded to that same database.

While in the OR, the time required for installing and dressing the catheters, functional assessments, and any complications during placement will be recorded. The surgical procedure and the total surgical time will also be recorded along with any relevant surgical complications.

Each subsequent day of the study (Day 1=24 hours, Day 2 =48 hours), the catheter will be assessed for following adverse events: Presence or absence of catheter dislodgement (catheter out or no longer in a clinically effective position), catheter occlusion, catheter leakage (presence of local anesthetic under occlusive dressing), skin irritation (presence of hyperemic cutaneous reaction not present at dressing placement), and catheter infection (presence of purulent material) by a member of the study team. Intubation status (including extubation time, where indicated), catheter boluses and catheter rate adjustments (if present) will be recorded. Patients' costs and charges will be collected electronically in order understand the healthcare value of this novel pain management strategy

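### A single case of neurologic symptoms lasting more than 3 days after removal halts enrolment, but the visible text schedules no study assessment that could confirm it; a minor gap, cheap to close

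*Combined protocol and SAP*

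**What the plan says.** Section I introduces its monitoring with "we will implement a rigorous system to follow and report any adverse events, including interim analyses by a non-blinded statistician, as described below". The rule that follows is "Enrollment will be halted and the IRB informed by the PI if any of the following conditions are met", and one serious event is enough. The serious list includes "Persistent neurologic symptoms lasting more than 3 days after a single shot block or catheter is removed".

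Section F sets out the scheduled follow-up: "Each subsequent day of the study (Day 1=24 hours, Day 2 =48 hours), the catheter will be assessed for following adverse events". The events listed are dislodgement, occlusion, leakage, skin irritation and infection. Intubation status, boluses and rate changes are recorded as well. Some data are "automatically collected via the Regional Anesthesia Outcomes Database", whose fields are not shown.

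Two other passages describe contact with patients. Section D(3) says that "all patients will be followed by the Acute Pain Service at BCH". The ropivacaine note in Section I says that patients are "further assessed for such daily by members of the research team and Acute Pain Service", where the reactions meant are hypersensitivity, allergic reaction, hypotension and arrhythmia.

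The primary criterion in Section E is a "successful intervention completion rate of 75% or greater of all subjects with no major adverse outcomes".

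**The concern.** A halting rule that one event can trigger needs a planned look for that event, at a time when it can have occurred. Here the two sections do not line up. Leakage, skin irritation and infection, which bear on the minor/moderate halting rule, each have a matching item on the daily check. The neurologic trigger, which is on the serious list, has none. Nor does Section F list the removal time, from which the 3 days are counted.

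What is at stake is the meaning of a report of no such events. If nobody is scheduled to ask, the absence of a report is weaker evidence than the absence of an event. Enrolment could also continue past a case that the sponsor has itself defined as a reason to stop. The pilot is meant to inform a randomised trial, so its safety statement will be carried forward.

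**Working it through.** The plan gives no figure of its own on this point, so the check is a comparison of times followed by a rough frequency.

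**1. When can the rule first be met?** The rule (Section I) needs symptoms for more than 3 days, which is 72 h, after removal. Hence earliest trigger = removal time + 72 h. The documents do not state a removal time, so a range is assumed. The last check named in Section F is at 48 h.

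| Removal (assumed) | Rule first met after | Time since the 48 h check |
|---|---|---|
| 0 h | 0 + 72 = 72 h | 72 − 48 = 24 h |
| 24 h | 24 + 72 = 96 h | 96 − 48 = 48 h |
| 48 h | 48 + 72 = 120 h | 120 − 48 = 72 h |
| 72 h | 72 + 72 = 144 h | 144 − 48 = 96 h |

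Section F can also be read as daily checks for as long as the catheter is in place, with Days 1 and 2 as examples. The last check then falls no later than removal, and the gap exceeds 72 h in every row. On either reading, no scheduled catheter check falls when the rule can be met.

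**2. Does other text supply the look?**
- Section F mentions functional assessments, but these are recorded in the operating room at placement.
- The daily ropivacaine assessment has no stated end, so it may continue after removal. Its listed items are drug reactions, none of them a persistent neurologic deficit.
- Acute Pain Service follow-up covers pain, catheter, infusion and opioid management. No neurologic item and no period after removal are stated.
- Section I's general commitment to track adverse outcomes gives no schedule or procedure for this event.
- A hematoma with pain or neurologic symptoms halts enrolment without the 3-day wait, but that is a different event.

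**3. How often might it arise?** Section C cites 0.93 per 1000 for any postoperative neurologic symptom, with more than 90% resolving within 1 month. The pilot has 10 patients and therefore 20 blocks, treated here as independent. The chance of at least one case in n is 1 − (1 − p)^n.
- Any symptom, p = 0.00093: 1 − (1 − 0.00093)^10 = 0.0093, and with n = 20, 0.0184.
- Lasting beyond a month, p below 0.1 × 0.00093 = 0.000093: below 0.00093 with n = 10, and below 0.0019 with n = 20.

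Symptoms lasting more than 3 days lie between these two lines. Unreported cases are a subset of all cases, so at the cited rate their chance cannot exceed 0.9% (10 patients) or 1.8% (20 blocks), whatever share is reported.

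**The case against.** **The visible text is not the whole protocol.** The opening instruction says that the CHeRP forms are part of it. Those forms, the case report forms, the outcomes database fields and the part between Sections L and N were not seen. Any of them could hold a neurologic item. This stands: the point concerns what the visible text schedules, and the sponsor can close it by showing that the item already exists.

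**Detection is not left to chance.** Adverse events are defined broadly enough to include neurologic ones. The Acute Pain Service is available around the clock, an investigator is on call, and the daily research-team contact has no stated end. Length of stay is not given, so many patients may still be inpatients at 96 to 144 h. This stands in part. A reader might infer that detection is purely passive, or that nobody sees the patient after removal, and the documents do not support either. They do support something narrower: nobody is scheduled to ask the question at the time that matters.

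**The effect is negligible.** The frequencies above are low, and even with perfect ascertainment 0 events in 10 patients leaves a one-sided 95% upper limit of 1 − 0.05^(1/10) = 25.9%. Ten patients cannot establish the rate of a rare event. This stands and lowers the severity. It does not remove the point, because the sponsor chose to make one case a halting event and gives the scarcity of prospective data as the reason for close monitoring.

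**A missed case would falsify the primary result.** A reader might infer this, since the criterion requires no major adverse outcomes. The term is not defined in the text, so the consequence holds only if it is taken to include the single-event halting list. That is a plausible reading, but it remains an assumption.

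**Conclusion.** The mismatch holds on the visible text. Section I sets a single-event halt that can first be met more than 72 h after removal, and no study assessment scheduled in Section F can confirm it. Detection depends on clinical follow-up or on family report.

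It is a minor safety gap. At the cited rate the chance of any neurologic symptom in the pilot is about 0.9% (10 patients) or 1.8% (20 independent blocks), and the qualifying event is rarer. That rate comes from regional anesthesia in anesthetized children generally. It does not bound the risk of bilateral blocks after pediatric sternotomy, for which Section C reports no prospective data. The conclusion assumes that the unseen material adds no neurologic follow-up. The timing result does not depend on the assumed removal times, because the rule falls after the last scheduled catheter check in every case. Sample size and the halting rule itself are unaffected.

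**What to change.** Amend Section F and leave the halting text in Section I as it is.

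1. Record the date and time at which each catheter is removed.
2. At removal, do a brief neurologic symptom check. Treat it as a baseline, because residual block is expected then.
3. On day 4 after removal, and more than 72 h after it, make one bedside or telephone contact. Ask about new numbness, weakness or any other neurologic symptom. If present, repeat until it resolves.
4. Count this contact as part of data collection, so that identifying information is not destroyed before it is closed.

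Do not add a daily numbness item while the infusion is running. It would flag the intended block and could not separate effect from injury.

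The cost is about ten short contacts (at an assumed 5 to 10 minutes each, 50 to 100 minutes in all), two form fields and a short amendment. If the last patient has no symptoms, data collection closes 4 days after that patient's catheter removal. That is at most about 4/243.5 = 1.6% of the planned 8 months. No extra patients are needed, and there is no hold between patients.

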#### **J. Quality Control Method**

Data quality control will be assured through automated and manual methods. The study database enhances data quality through required entry fields for critical data and automatic flags for missing or out-of-range data. Efforts will be made to minimize data entry error by the development of a user-friendly database and all data entry will be double-checked with the source files. Data will be audited for accuracy by investigators after being entered into the database.

#### **K. Data Analysis Plan**

At the time of data analysis, datasets will be downloaded from the standard, secure database and merged into Statistical Analysis Systems 9.3 (or more recent) for purposes of analysis. Missing data will be accounted for when the data is coded into respective variables.

Descriptive statistics will be generated in order to summarize demographic characteristics of patients enrolled. Data will be evaluated subsequently with regard to the above-mentioned criteria for 'feasibility.'

Adverse events and complications (if any) associated with the blocks will be recorded and categorized.

Matched groups will be compared for demographic data, Patients costs and charges, risk factors, diagnosis, procedure, and cardiopulmonary bypass and clamp times to ensure their similarities. Once data collection is complete, identifying information will be destroyed.

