### **(3) Description of Study Treatments or Exposures/Predictors**

Participants will have their medical record reviewed following enrollment for demographic information including: gender, age, weight and height, procedure, surgeon, laterality (if applicable), and current and historical medication use.

Enrolled patients will have bilateral erector spinae blocks (with catheters for postoperative local anesthetic infusion) placed by the investigators in a sterile fashion after of the surgical procedure is complete as follows:

- The patient is placed in a lateral decubitus position (left or right), with all pressure points padded in routine fashion.
- The area for intervention is prepped with a chlorhexidine solution, and sterile drapes are applied to demarcate the block placement area.
- The T4/5 transverse process on one side is identified with the ultrasound transducer in a parasagittal orientation.
- An 18g Tuohy needle is advanced to the target area under direct ultrasound visualization. The needle tip is advanced until it contacts the transverse process, just below the erector spinae muscle complex.
- Normal saline is injected to confirm appropriate needle tip position. The erector spinae muscle is visualized to be elevated up off of the transverse process with normal saline injection
- With confirmation of appropriate needle tip position, the initial local anesthetic bolus is injected using a weight-based dosing protocol (generally 0.75ml/kg of straight 0.2% ropivacaine).
- Following the bolus injection, a catheter is threaded into the space occupied by the local anesthetic bolus.

- Catheter tip position is verified by one or more of the following: ultrasound visualization of the catheter tip, ultrasound visualization of instilled normal saline and/or ultrasound visualization of a small hyperechoic (i.e. bright on ultrasound) injection of air.
- With the catheter tip position identified, the catheter is tunneled to a cutaneous exit point approximately 2-3cm from the incision using a Crawford needle.
- The catheter is dressed in standard fashion with an adhesive catheter anchor, Dermabond, Mastisol, Tegaderm and tape.
- This is repeated for the contralateral side. To the extent possible, this will be done without repositioning in a contralateral decubitus position.
- A label indicating that each catheter is a nerve-block catheter with its laterality and date of placement noted is applied to each catheter.
- Catheter placement is complete.

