## **H. Study Timeline**

We plan to enroll a total of 10 patients in the pilot study. We will then match enrolled patients from the pilot study to patients within the enhanced recovery after cardiac surgery (ERAS Cardiac) program (IRB # P00029161) in a 1:2 ratio for a total of 30 patients altogether. All patients in this study will already be part of the enhanced recovery after cardiac surgery clinical program (a quality improvement program). We anticipate that it would take approximately 8 months to complete enrollment and data collection for this study.

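### Section K limits the adverse event summary to block-associated events, while Section I defines and tracks events regardless of cause, and no attribution procedure is given

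*Combined protocol and SAP*

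**What the plan says.** Section I (Adverse Event Criteria and Reporting Procedures) gives the definition: "An Adverse Event refers to any untoward medical occurrence whether or not it is considered intervention-related". Its monitoring subsection sets the population: "Adverse outcomes will be carefully tracked for all patients enrolled in the study". Enrolment stops on "1 of any of the following serious adverse events". That list includes death and pneumothorax, with no condition that either be attributed to the block.

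Section K (Data Analysis Plan) touches safety in two places. One is the feasibility evaluation: "Data will be evaluated subsequently with regard to the above-mentioned criteria for 'feasibility". The primary criterion behind it, in Section E, is a "successful intervention completion rate of 75% or greater of all subjects with no major adverse outcomes", again with no mention of cause. The other is the only sentence in Section K that plans a summary of adverse events: "Adverse events and complications (if any) associated with the blocks will be recorded and categorized".

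No section states who judges association with the block, when, or by what criteria. Section D(3) says the blocks are "placed by the investigators in a sterile fashion". Section F has a study team member make the daily catheter checks.

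**The concern.** The scope of collection and the scope of the planned summary differ, and what separates them is a causal judgement with no rule behind it. These are sternotomy patients, mainly having cardiac surgery. A death, a pneumothorax, hypotension or an arrhythmia could plausibly follow from the operation or from the block, so attribution will often be open to argument. Every enrolled patient receives the block, so whoever judges relatedness knows the treatment.

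At stake is the descriptive safety result that this pilot passes on to the planned randomised trial. If a debatable event is classed as surgical, a reader of the Section K summary would not see it, nor learn that a judgement had been made.

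**Working it through.** The documents give no event rate, interval or power figure on this point, so there is no stated result to reproduce. The check is mainly one of text.

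**1. Follow one event through the plan.** Take a pneumothorax in an enrolled patient.

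| Place | Does it count? | Depends on attribution? |
|---|---|---|
| Section I, definition | Yes | No |
| Section I, tracking | Yes | No |
| Section I, halting rule | Yes, one is enough | No |
| Section E, primary criterion | Yes, if regarded as major | No |
| Section K, adverse event summary | Only if judged block-associated | Yes |

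The last row is the only one where a causal opinion decides inclusion. The same holds for a death. Several other halting items (site haematoma, site bleeding, leakage, skin reactions) are tied to the block or catheter by definition, so the mismatch matters little for them.

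**2. Look for another planned summary that would show the event.** Section F records relevant surgical complications along with the surgical procedure and surgical time, but plans no table of them. Its daily list covers catheter problems. Section I promises interim analyses by a non-blinded statistician, to be described below it; what follows is halting and reporting rules, with no analysis. Reporting to the DSMB, the IRB and the quality assurance physician does not determine the content of the final summary. No all-cause table is planned anywhere.

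**3. Size of one attribution decision.** Input: n = 10 (Sections D(1), H and L). The exact one-sided 95% upper limit solves P(X ≤ x | n, p) = 0.05.

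- One event counted: 1/10 = 10%. Solving (1 − p)^10 + 10p(1 − p)^9 = 0.05 gives p = 0.394.
- Event left out: 0/10 = 0%. Solving (1 − p)^10 = 0.05 gives p = 1 − 0.05^(1/10) = 0.259.

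The two-sided exact 95% intervals are 0.3% to 44.5% and 0% to 30.8%. The denominator is 10 only if the event occurs in the last patient or the IRB lets enrolment continue. If enrolment stops after k patients, the contrast is 1/k against 0/k.

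**4. How often the question could arise.** Suppose events of debatable cause occur in a fraction q of patients. This is an assumption; the documents give no such rate. The chance of at least one in 10 patients is 1 − (1 − q)^10:

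- q = 2%: 0.18
- q = 5%: 0.40
- q = 10%: 0.65

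These are chances that such an event occurs, not that it is misattributed or dropped.

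**The case against.** The strongest reply is that Section K does not say other events are excluded. It says block-associated ones will be recorded and categorised, and the qualifier could even be read as attaching to complications alone. Surgical complications are recorded under Section F, and serious events go at once to the DSMB and IRB. On that view this is loose drafting of one descriptive sentence in an unpowered pilot.

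Much of this stands. It limits the consequence and shows that events would not vanish from the records. It does not supply a planned all-cause summary or an attribution rule, and if the broader reading was intended, the plan should say so.

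A reader might infer three stronger points, which the documents do not support:

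- **That calling an event unrelated removes it from the feasibility verdict.** The primary criterion has no relatedness condition, and Section K evaluates it in a separate paragraph from the adverse event sentence. What counts as major is undefined, but that is a different gap.
- **That the operators decide attribution.** No assessor is named. Investigators place the blocks, but the daily checker is not said to be the operator, and the ropivacaine note in Section I also involves the primary anesthesiologist and the Acute Pain Service. The defect is the silence.
- **That the matched patients should supply background event rates.** Section H matches "in a 1:2 ratio for a total of 30 patients altogether", which is 10 + 2 × 10 = 30, and Section K compares the groups mainly to check similarity. Record review of 20 patients set against prospective daily checks would give unequal ascertainment, and even 0/20 has a one-sided 95% upper limit of 1 − 0.05^(1/20), about 14%.

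**Conclusion.** The mismatch is real and limited. Taken literally, Section K yields a safety summary filtered by cause from events that Section I defines and tracks without regard to cause, and nobody is assigned to apply the filter. At n = 10, one exclusion changes the reported result from 1/10 to 0/10 and lowers the upper limit from 39.4% to 25.9%. This rests on reading the qualifier as covering adverse events as well as complications, and on all 10 patients being enrolled. The limits only show scale.

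The wording affects the descriptive summary alone. The primary feasibility criterion and the halting rule are unaffected, and the point does not invalidate the pilot. It is worth correcting because an event serious enough to stop enrolment should not be able to drop out of the final safety table.

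**What to change.** Replace the adverse event sentence in Section K with, for example: *All adverse events as defined in Section I, including every halting event, are tabulated by patient for all enrolled patients regardless of cause; judged relation to the block is shown in a separate column and does not remove an event.* State beside it who makes that judgement and on what criteria.

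The cost is a sentence or two and a slightly longer, less favourable event table. Because Section I says reports will be aggregated, the published version can give counts of patients with each event, split by judged relation. No data collection in the matched patients is needed.
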